7.4 Reporting Procedures

AE Reporting: All AEs will be collected on an Adverse Event Form in electronic format and recorded in the RedCap database. All AEs experienced by the participant will be reported in Safety Reports sent twice a year to the NINDS Program Official.

SAEs Reporting: When SAEs occur that are unanticipated (i.e., events other than those described in the protocol, consent form and DSMP), and that are related to the intervention, they will be reported to NINDS Program Officer within 48 hours of study's knowledge of the SAE. The expedited report will be followed by a detailed, written SAE report as soon as possible. Follow up information may be required.

Relatedness: The potential event relationship to the study intervention and/or participation is assessed by the site investigator. The comprehensive scale to categorize an event is listed below:

- Definitely Related: The AE is clearly related to the investigational procedure – i.e. an event that follows a reasonable temporal sequence from administration of the study intervention, follows a known or expected response pattern to the suspected intervention, that is confirmed by improvement on stopping and reappearance of the event on repeated exposure and that could not be reasonably explained by the known characteristics of the subject's clinical state.
- Possibly Related: An AE that follows a reasonable temporal sequence from administration of the study intervention follows a known or expected response pattern to the suspected intervention, but that could readily have been produced by a number of other factors.
- Not Related: The AE is clearly not related to the investigational procedure - i.e. another cause of the event is most plausible; and/or a clinically plausible temporal sequence is inconsistent with the onset of the event and the study intervention and/or a causal relationship is considered biologically implausible.

Expectedness: AEs must be assessed as to whether they were expected to occur or unexpected, meaning not anticipated based on current knowledge found in the protocol and the consent form. Categories are:

- **Unexpected:** The nature or severity of the event is not consistent with information about the condition under study or intervention in the protocol or consent form.
- **Expected:** The event is known to be associated with the intervention or population under study.

Classification of AE Severity:

- **Mild:** Awareness of signs or symptoms, but easily tolerated and are of minor irritant type causing no loss of time from normal activities. Symptoms do not require therapy or a medical evaluation; signs and symptoms are transient – i.e. no doctor visit or medical treatments were required.
- **Moderate:** Events introduce a low level of inconvenience or concern to the participant and may interfere with daily activities, but are usually improved by simple therapeutic measures; moderate experiences may cause some interference with functioning – i.e. minimal medical treatment was needed, possible doctor visit or physical therapy.
- **Severe:** Events interrupt the participant's normal daily activities and generally require systemic drug therapy or other treatment; they are usually incapacitating – i.e. medical attention was required, possible hospitalization.

Note: Severity is not synonymous with seriousness. SAEs are a subset of the reported AEs.

7.5 Follow-up for Adverse Events

AEs will be followed until the participant discontinues the study.

7.6 Safety Monitoring

Prior to beginning data collection, we will convene an internal safety monitoring committee who will be responsible for monitoring participant safety and study progress. The committee will be comprised of investigators on the project team. Before beginning recruitment, [name] and the safety committee will reconfirm that our sites have appropriate safety measures in place. The internal safety monitoring committee will meet with the entire research team to review the study protocols. Particular attention will be paid to outcome definition, study design, procedures for recording and reporting adverse events, informed consent procedures and documentation.

At the initial meeting, the internal safety monitoring committee may recommend modifications or clarification of the protocol, and it will formulate its operating procedures (e.g., meeting schedule, reports due dates for the study statistician, unblinding policy, and what interim data may be released to the investigators). At the initial meeting the plans for interim monitoring for efficacy and futility will be presented to the internal safety monitoring committee as an aid for monitoring the trial.

We will train competent staff to conduct the assessments, ensure they understand the data collection procedures and process, and understand adverse event reporting requirements.

Trained clinical assistants, who will monitor the subject for any adverse events, will perform all assessments. We do not expect any serious adverse events during these non-invasive interventions. The clinical assistant will stop the testing procedures if subjects feel stressed or get embarrassed by their performance, and relay the information immediately to [name] or one of the supervising clinicians (Drs. [name], [name], [name], or [name]). In addition, [name] and/or [name] will be available at the clinic site during the conduct of the trial, and [name] will be available by cellular telephone at all times to address any safety concerns or clinical issues.

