9.2 Sample Size and Randomization

This randomized study has 600 subjects for each of the 2 groups. Assuming a non-completion rate of EMR entries of 10% over 90 days and that 25%, 30% or 35% of control subjects will experience ‘improved dementia care,’ we can detect odds ratios of 1.46, 1.43 or 1.42, respectively, on the effect of 5-Cog on improving dementia care with 80% power using a two-sided test with significance level of 0.05. There is a paucity of studies examining efficacy of brief cognitive screens in primary care. One non-randomized trial of

screening by medical assistants coupled with a decision tree in primary care clinics showed new physician action in 17% of patients with a positive screen in intervention sites compared to 1% in control sites.³⁶ Action included new dementia diagnosis, referral to specialist or initiating dementia treatment (similar to our primary outcome). While our projected effect size used for sample size estimation is conservatively lower than that reported in this previous study,³⁶ the effect size from this previous study was not used to calculate power given its preliminary, non-randomized nature but is presented in support of our assumptions. A review of 8 studies of detection of mild dementia in primary care showed that sensitivity ranged from 9% to 41%.⁵⁵ Detection rates in clinics are even lower for earlier dementia stages such as MCI.⁵⁶ These observations support our assumptions of lower rates of improved dementia care in our control group.

Cohort retention: This is not a major issue for this RCT as primary outcomes are based on clinical encounters information collected from EMR and other administrative data sources in patients residing in Bronx County and receiving primary care in our institution. Also, primary outcomes do not require repeat in-person testing after baseline assessments.

- *Non-completion:* We realize that not all patients will complete the additional tests described above as covariates or exploratory outcomes. We will complete as many of the tests as possible depending on patients' availability. Nonetheless, our overall sample size of 1,200 participants provides a sufficient pool to conduct sensitivity analyses assuming non-completion rate of 50%.

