9.2.1 Treatment Assignment Procedures

Patients will be assigned to screening using stratified block randomization. [name], who is not involved in subject testing or interventions will generate a computerized block randomization scheme to assign study identification numbers to either 5-Cog or control arms. Patients will be stratified by gender and age (< or >75 years). Briefly, an encrypted file containing the group assignment is prepared for each study identification number. The file is stored in RedCap the database program used for this trial. The assignments are presented to the research assistants (RA) in sequential order at the time the participant is enrolled, following the eligibility assessment, and

administer the indicated screen. Participants and the RA who administers the tests are not blinded to group assignment. However, investigators, data analysts collecting outcome data, and the statistician remain blinded to individual assignments.

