9.3 Interim analyses and Stopping Rules

Due to the non-invasive nature of the protocol, it is not expected that early termination will be required due to adverse events. However, constant monitoring of the participants by [name], other investigators, and research staff will be maintained to ensure that AEs are not occurring. Early study termination will occur in the event of any unanticipated serious adverse event determined to be possibly, probably or definitely related to study procedures.

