9.5 Data Analyses

We will examine data for potential outliers and analyze the robustness of our findings

against them. We will perform per-protocol analysis to assess the sensitivity of our findings to protocol deviations. Furthermore, the impact of baseline imbalance will be determined by comparing the analysis outcomes with and without controlling for baseline attributes. Chi-square test will be used to compare ‘improved dementia care’ outcome within 90 days post-intervention between the intervention and control groups. Logistic regression model adjusted for covariates will also be used. We will use **intention to treat analysis**.⁵⁷ Pre-specified baseline covariates to account for **confounders** in the planned analysis include age, gender, education, and chronic illnesses. Baseline distribution of covariates will be compared to assess adequacy of randomization. We do not discount residual/unmeasured confounding – though this is more of an issue in observational studies without randomization. We will report adjusted and crude estimates of associations to assess confounding, and discuss limitations of the study.

Primary outcome: Chi-square test will be used to compare ‘improved dementia care’ outcome within 90 days post-intervention between the intervention and control groups. Logistic model adjusted for covariates will also be used.

Heterogeneity of treatment effect (HTE) is the nonrandom, explainable variability in the direction and magnitude of treatment effects for individuals within a population. The main goals of HTE analysis are to estimate treatment effects in clinically relevant subgroups and to predict whether an individual might benefit from a treatment. In this RCT, we will specifically address HTE due to gender (male/female), ethnicity (African-American/Hispanic/Caucasian) and education (less than high school/ high school graduate). Treatment effects in these subgroups will be evaluated using stratified analysis. Alternative, an interaction term between the subgroup characteristic and treatment group will also be tested.

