10.3.4 Monitoring

A study protocol, Manual of Operations and DSMP for all study activities will be developed during study setup and approved by the IRB and internal safety monitoring committee prior to initiating recruitment. Data will be maintained in a Database Manager System (RedCap).

The database system will have automated checks for ranges of values and logical validity of data entered and will be programmed to import subject data directly from the computerized test data files. Imported data files will be checked for data integrity and flagged in the event of inconsistent or missing data. Hand entered data will be verified using double entry routines to guard against key punch errors. This system will provide

immediate access to individual subject data and can generate a summary report of the entire database. The database will contain provisions for password protection and distribution of analytic data files containing only necessary information on an as-needed basis; there will be an interface to export all or selected data from RedCap and transfer these to any of the statistical packages (SAS, S-PLUS, Stata, SPSS) used by the project investigators.

Full backups of the entire database will be performed daily. For added security, copies of the databases are kept in two separate physical locations in locked, fire-resistant containers. Database files will be maintained by the Database Management Core and subjected to quality control procedures. Summary reports will be generated and reviewed by the project manager and PI as requested.

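### Does the mention of interim efficacy and futility monitoring in section 7.6 leave the trial's 0.05 test without type I error control?

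*Combined protocol and SAP*

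**What the plan says.** Five parts of the combined protocol and SAP bear on this.

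- **7.6 Safety Monitoring** sets up an internal safety monitoring committee: "The committee will be comprised of investigators on the project team". At its first meeting it writes its own operating procedures, including "reports due dates for the study statistician, unblinding policy, and what interim data may be released to the investigators". The sentence at issue follows: "At the initial meeting the plans for interim monitoring for efficacy and futility will be presented to the internal safety monitoring committee". The section calls this an aid to monitoring. It gives no number of looks, timing or boundary.
- **9.3 Interim analyses and Stopping Rules** deals with adverse events only: "Early study termination will occur in the event of any unanticipated serious adverse event", if judged related to study procedures. It contains no efficacy or futility rule.
- **9.2 Sample Size and Randomization** sizes the trial once, "with 80% power using a two-sided test with significance level of 0.05".
- **9.5 Data Analyses** compares the primary outcome by chi-square "within 90 days post-intervention between the intervention and control groups", and adds a covariate-adjusted logistic model. No interim test and no adjusted final level appear.
- **9.2.1 Treatment Assignment Procedures**, like 5.2 and 6.2.2, says that "investigators, data analysts collecting outcome data, and the statistician remain blinded to individual assignments".

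Section 10.3.4 refers to companion documents that are not part of the material: "A study protocol, Manual of Operations and DSMP for all study activities will be developed during study setup". They need approval by the IRB and the committee before recruitment starts.

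**The concern.** Section 7.6 speaks of the plans for efficacy and futility monitoring as if they exist, yet the section whose title promises interim analyses does not hold them. If the committee compared the arms on the primary outcome and could stop for benefit, a final test at the full 0.05 would be too liberal. The people seeing the comparison would also be running the trial. The blinding statements cover individual assignments and do not expressly rule out summaries by arm.

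Looks would be feasible. Enrolment takes 30 months of a 42-month trial, the outcome is known at 90 days, and section 10.2 freezes data sets twice a year. At stake would be the meaning of the final p-value and the neutrality of the trial team.

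**Working it through.** **1. What the plan schedules.** Read together, 9.3 lists no efficacy or futility look, 9.2 sets aside no alpha for one, and 9.5 has no interim test. Section 7.6 says only that plans will be shown to the committee. No passage says that a comparison by arm will be made, or what would follow from it.

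**2. Is 9.2 a single-analysis calculation?** The inputs are all from 9.2: 600 per arm, 10% non-completion, control rates of 25%, 30% and 35%, two-sided 0.05 and 80% power.

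- Evaluable per arm: n = 600 × 0.9 = 540.
- Intervention rate: p2 = OR·p1 / (1 − p1 + OR·p1).
- Power = Φ{[(p2 − p1)√n − 1.96·√(2p̄(1 − p̄))] / √(p1(1 − p1) + p2(1 − p2))}, where p̄ = (p1 + p2)/2.

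For p1 = 0.25 and OR = 1.46:

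- p2 = 0.365/1.115 = 0.3274 and p̄ = 0.2887.
- The numerator is 0.07735 × 23.238 − 1.96 × 0.6408 = 0.541, and the denominator is 0.6385.
- The ratio is 0.848, so power is 80.2%.

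| Control rate | Stated OR | Power at stated OR | Detectable OR at 0.05 | Detectable OR at 0.048 |
|---|---|---|---|---|
| 25% | 1.46 | 80.2% | 1.459 | 1.462 |
| 30% | 1.43 | 79.3% | 1.434 | 1.438 |
| 35% | 1.42 | 80.2% | 1.419 | 1.422 |

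All three stated values reproduce at 0.05. At 0.048, the final level after one O'Brien-Fleming look, the middle value would round to 1.44. Only that value separates the two levels, so this evidence is modest. It does agree with 9.3 and 9.5: the trial was sized for one test that uses all of the 0.05.

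**3. Type I error under different assumptions about looks.** The documents give no number of looks, so the number is an assumption. With one interim look at half information, the two Z statistics have correlation √0.5 = 0.707. The chance of crossing ±1.96 at least once is 0.05 + 0.05 − P(both) = 0.10 − 0.0169 = 0.0831. The other rows come from numerical integration over successive looks.

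| Assumption | Overall type I error |
|---|---|
| No between-arm look (9.2, 9.3 and 9.5 as written) | 5.0% |
| Non-binding futility look only | at most 5.0% |
| Interim boundary of 3.29 in absolute Z, one to four interims, final 1.96 | 5.0% to 5.1% |
| One unadjusted look at 25%, 50% or 75% information | 9.1%, 8.3% or 7.3% |
| Two, three or four unadjusted, equally spaced looks | 10.7%, 12.6% or 14.2% |

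**4. What a formal look would cost.** Take one look at half information. Classical O'Brien-Fleming boundaries are 2.797 and 1.977, with final level 0.048. The Lan-DeMets spending version has 2.963 and 1.969, with final level 0.049. At the effect giving 80% power in a fixed design, the drift is 1.960 + 0.842 = 2.802. Under the classical boundaries the final test alone then has power Φ(2.802 − 1.977) = Φ(0.825) = 79.5%, and the whole design 79.7%. If the unseen plans hold a conventional look of this kind, the effect on sections 9.2 and 9.5 is small.

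**The case for a change.** The best case for a change is that silence is not a prohibition. Section 7.6 refers to efficacy monitoring as planned, and section 9.3 neither describes it nor rules it out. A committee of investigators that sets its own unblinding policy is a weak barrier, since it would be deciding what to release to its own members. Neither 7.6 nor 9.3 points to the DSMP or the Manual for interim rules, and a final level other than 0.05 would belong in 9.2 and 9.5. The amendment log records no change to 7.6 or 9.3. Low safety risk justifies an internal safety committee, but does not by itself justify giving it efficacy data.

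Part of this stands. The two sections do not match, and the documents name no reviewer of between-arm efficacy data from outside the team.

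The stronger reading does not stand. Presenting plans to a committee is not the same as testing. The documents have some safeguards: an unblinding and data-release policy, blinding of the investigators and the statistician to individual assignments, twice-yearly safety reports to the NINDS Program Official (7.4), and the power of the IRB and NINDS to discontinue the study (11.4). The last two have no stated role in efficacy. None of these replaces an alpha-spending rule, but no such rule is needed unless an efficacy look is made.

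**Conclusion.** No change to the plan follows. The mismatch between 7.6 and 9.3 is real, but it is missing detail on an activity that the plan never schedules. An analyst working from 9.2, 9.3 and 9.5 would make the primary comparison once, after the 90-day windows have closed, at two-sided 0.05. That test is sound, with type I error of 5.0%.

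The range of 7.3% to 14.2% applies only if efficacy looks outside the written plan were made and each was tested at 0.05 without adjustment. No passage supports even one such look.

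The conclusion rests on two assumptions: that no unadjusted efficacy look was made, and that any interim plan in the DSMP or Manual carries its own boundary. With one O'Brien-Fleming look at half information, the final level would be 0.048 or 0.049 and the loss of power about 0.3 point for the whole design. The remaining question, whether any between-arm look took place, is a minor clarification that the report of results can answer.

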8 INTERVENTION DISCONTINUATION

Subjects may withdraw voluntarily from participation in the study at any time and for any reason. However, participants will continue to be followed, with their permission, as long as they completed the 5-Cog or health literacy and grip strength assessments.

9 STATISTICAL CONSIDERATIONS

9.1 General Design Issues

We propose to conduct a single-blind RCT to validate the 5-Cog battery coupled with decision tree in an ethnically diverse Bronx primary care population of 1,200 older patients with cognitive concerns. We chose an active control (health literacy and grip) to balance time and tester exposure in the 5-Cog arm. Our primary outcome is improved dementia care.

Primary Outcome: The primary outcome is improved dementia care, defined as meeting any one of the following endpoints within one month of the clinic visit at which the patient was randomized.

1. New diagnosis of dementia (relevant ICD-10 codes) or MCI (331.83) documented in the EMR. The recent DSM-V criteria include categories of ‘major neurocognitive disorder’ and ‘mild neurocognitive disorder,’ which overlap with dementia and MCI. We will track these diagnoses but not use these solely to define the outcome as they are as yet not being widely used as diagnostic or billing codes in our primary care sites.
2. Tests ordered for reversible causes of cognitive impairment as recommended by published guidelines of professional societies (e.g. thyroid function tests, B-12 level, CT or MRI scans).
3. New prescriptions for medications for dementia or MCI indications in EMR.
4. Referral for specialist evaluation for cognitive impairment (Neurology, Geriatrics or Psychiatry) in EMR.

9.2 Sample Size and Randomization

This randomized study has 600 subjects for each of the 2 groups. Assuming a non-completion rate of EMR entries of 10% over 90 days and that 25%, 30% or 35% of control subjects will experience ‘improved dementia care,’ we can detect odds ratios of 1.46, 1.43 or 1.42, respectively, on the effect of 5-Cog on improving dementia care with 80% power using a two-sided test with significance level of 0.05. There is a paucity of studies examining efficacy of brief cognitive screens in primary care. One non-randomized trial of

screening by medical assistants coupled with a decision tree in primary care clinics showed new physician action in 17% of patients with a positive screen in intervention sites compared to 1% in control sites.³⁶ Action included new dementia diagnosis, referral to specialist or initiating dementia treatment (similar to our primary outcome). While our projected effect size used for sample size estimation is conservatively lower than that reported in this previous study,³⁶ the effect size from this previous study was not used to calculate power given its preliminary, non-randomized nature but is presented in support of our assumptions. A review of 8 studies of detection of mild dementia in primary care showed that sensitivity ranged from 9% to 41%.⁵⁵ Detection rates in clinics are even lower for earlier dementia stages such as MCI.⁵⁶ These observations support our assumptions of lower rates of improved dementia care in our control group.

Cohort retention: This is not a major issue for this RCT as primary outcomes are based on clinical encounters information collected from EMR and other administrative data sources in patients residing in Bronx County and receiving primary care in our institution. Also, primary outcomes do not require repeat in-person testing after baseline assessments.

- *Non-completion:* We realize that not all patients will complete the additional tests described above as covariates or exploratory outcomes. We will complete as many of the tests as possible depending on patients' availability. Nonetheless, our overall sample size of 1,200 participants provides a sufficient pool to conduct sensitivity analyses assuming non-completion rate of 50%.
- *Over- or under-detecting cognitive impairment:* Given the high sensitivity and validity of 5-Cog procedures for dementia detection, we do not expect under-detection to be a major issue. We will set PMIS cutscores to maximize sensitivity and will improve cognitive concern ascertainment. A major consequence of over-detection is the strain on limited primary care resources resulting from more dementia assessments. Our decision tree provides guidance to primary care physicians regarding next steps in cognitively impaired patients. Red flags are built within our decision tree to channel patients for specialist evaluations. These steps were developed in consultation with our primary care partners. We will carefully monitor clinical, logistical and economic impact of introducing 5-Cog in our primary care sites, and make any necessary system changes to optimize clinical encounters. It is encouraging that introducing PMIS into our local EMR has not resulted in significant bottlenecks or overburdening specialists. We have also not observed any significant bottlenecks or negative feedback from primary care staff regarding implementing the first phase of the 5-Cog battery at our site.

